## 8 STUDY ASSESSMENTS AND PROCEDURES

## 8.1 EFFICACY ASSESSMENTS

Screening procedures and evaluations may be performed on the day of enrollment but no more than 10 days prior to the day of enrollment. The screening process will be a discussion with the patient and review of medical history and height and weight to determine eligibility, and explanation of the study rational and study protocol, and demonstration of the two dressing options. Informed consent will then be obtained and patients will have the opportunity to ask questions.

The study intervention will be administered at the end of the scheduled cesarean delivery procedure. Standard dressings will be removed on postoperative day 1 as per current protocol and PICO NPWT dressings will be changed if necessary in the hospital and removed on postoperative day 5 by the patient at home.

**Procedures that will be completed during the study as part of regular standard of clinical care:** the post-operative visits on day 7 – 14 and 42 +/- 10 days are part of regular standard of clinical care and the outcomes and incision assessments after the participating patients leave the hospital will be performed by skilled residents and attending physicians at these visits. Charts will be reviewed to ascertain if SSO/SSIs were diagnosed or SII were necessary.

During these regularly scheduled visits, a **physical examination and incision assessment** will be performed including weight, abdominal exam, incision exam, and all regular postoperative visit exams including breast and pelvic (at the 42 +/- 10 day visit only) as part of the routine standard of care.

If follow-up visits or unscheduled visits are required for treatment of SSO/SSIs or SII, information regarding the type of SSO or SII required will be obtained from review of the medical chart.

**Surgical Site Occurrences include:** unanticipated local inflammatory response, prolonged drainage, fluid collection, dehiscence, surgical site infection (SSI). SSI is diagnosed using the following criteria: warmth to touch, pain with palpation, skin redness, irritation, or induration, large amount of drainage or purulent drainage, fluctuance suspicious for wound abscess, fever, and/or wound odor.

**Surgical Site Interventions include:** Antimicrobials for surgical site infection, surgical drainage of the incision, surgical incision packing, adjunctive negative pressure therapy, debridement, or re-operation.

Information that will be obtained through review of existing data:

- Age
- BMI (kg/m^2)
- Medical comorbidities
- Pregnancy history (term, preterm, abortions, and living history)
- Mode of prior deliveries, if applicable
- Indication for cesarean delivery
- Incision assessment information from residents and attendings at follow-up visits.

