## 4 STUDY DESIGN

### 4.1 OVERALL DESIGN

Hypothesis: We hypothesize that the PICO NPWT dressing will decrease the incidence of surgical site infections and occurrences in patients with a BMI  $\geq 35 \text{ kg/m}^2$  undergoing cesarean delivery.

Trial phase: 3

Description of trial design: A randomized, controlled, single-institution, interventional clinical trial to evaluate clinical outcomes.

Methods used to minimize bias:

Selection bias will be minimized by reducing the exclusion criteria to include all eligible subjects. Also, the randomization sequence will be concealed from investigators at the time of obtaining consent from the trial participants.

There will be no blinding in the study. Neither the participants nor the physicians will be blinded to the study treatment they are randomized to.

Masking or blinding is not feasible in this study because the size, shape, and components of the PICO and standard dressings are different as is the length of time each dressing is worn. However, participant ascertainment bias will be minimized because diagnosis of an SSO/SSI and need for SII will be made and determined by skilled resident and attending physicians at each of the routine visits, not by patient report. Co-intervention bias will be minimized because there will be no changes in routine post-operative or nursing care instructions between groups.

The statisticians who are responsible for analyzing the results will not be made aware which group received the PICO NPWT dressing versus the standard wound dressing.

Recruitment bias will be minimized by ensuring that all participants who meet inclusion and exclusion criteria with a planned cesarean delivery during the specified time frame are approached and offered participation in the study. Most hospitals utilize standard of care wound dressings similar to the dressing described for the standard dressing group in this proposal, which will minimize clinical practice bias.

Number of study groups/arms: There will be two study groups, Group 1 will be randomized to receive the standard of care pressure dressing and Group 2 will be randomized to receive the PICO NPWT dressing postoperatively.

Study intervention duration: The study period will begin with the day of the scheduled cesarean delivery procedure and end 42 +/- 10 days postoperatively.

Name of study intervention: The Smith & Nephew PICO single-use negative pressure wound therapy system.

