### 6.3 MEASURES TO MINIMIZE BIAS: RANDOMIZATION AND BLINDING

This trial tests a clinical intervention that is not amenable to protection against performance bias through the blinding of participants, clinical staff or data collectors. There will be no blinding in the study. Neither the participants nor the physicians will be blinded to the study treatment they are randomized to.

The Biostatistics Unit at the Feinstein Institute for Medical Research [BU-FIMR] will develop a randomization plan for the study using the Biostatistics Randomization Management System [BRMS]. BRMS is a secure, HIPAA-compliant, web-based application that allows investigators to randomize subjects into randomized clinical trials (RCTs) using a personal computer with internet access. The BRMS allows for multi-center, stratified, and single/double blinded RCTs. Randomization notifications are automatically sent to the PI and other authorized personnel. BRMS maintains compliance in RCTs.

A randomization schema will be generated by the BU-FIMR using the method of permuted blocks. Subjects will be randomly assigned in a 1:1 ratio to either 'PICO' or 'STANDARD DRESSING'. Details of the randomization procedure, including required record keeping will be further developed upon approval of the protocol.

The RA will randomize participants in the operating room at the start of their cesarean procedure and advise the operating obstetrician and nursing staff of the allocated treatment as close to the end of the procedure as possible in order to minimize performance bias.

To minimize the potential for outcome detection bias, an expert statistician, blinded to group allocation, will assess the data to determine the primary outcome.

Subjective outcomes (SSI/SSOs) are reported by patients or observed by study personnel, who cannot be blinded because they need to check the dressings.

Outcome assessors will be masked to allocation.

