## 8.2 SAFETY AND OTHER ASSESSMENTS

Sequence of events that will occur during screening process:

1. Review of scheduled cesarean delivery schedule for the day.
  - a. Screening procedures must be performed within 10 days of study enrollment.
2. Review of medical charts to assess for eligibility (see below).
3. Approach patient and explain trial and interventions.
4. No dietary or activity considerations are required for participation in the trial; however, patients will be counseled that the PICO dressing protocol requires the dressing to be in place for a minimum of 5 days.
5. Assessment of ability to comply with study intervention.
6. Obtain consent.
7. The patient will not be randomized until presentation to labor and delivery and randomization group will not be exposed to healthcare team until as close as possible to the end of the surgical procedure.

Information that will be obtained through review of existing data (i.e. patient's medical chart):

- Age
- BMI (kg/m^2)
- Medical comorbidities
- Pregnancy history (term, preterm, abortions, and living history)
- Mode of prior deliveries, if applicable
- Indication for cesarean delivery
- Incision assessment information from residents and attendings at follow-up visits

No study specific procedures will be performed and so no results will be provided to patients.

List and description of the following procedures/evaluations, as applicable:

- **Physical examination:** height and weight, fundal height, fetal heart rate measurement (initial study day prior to administration of intervention, and incision assessment).
- **Vital signs:** temperature, pulse, and blood pressure.
- **Assessment of adverse events.** Adverse events will be followed by attending physicians and research PI [name]. There are minimal expected adverse events that are not beyond the potential adverse events that could occur from the regular standard dressing (i.e. dressing tape site reaction or allergy to tape)

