#### 9.4.2 ANALYSIS OF THE PRIMARY EFFICACY ENDPOINT(S)

Primary endpoint: the incidence of postoperative surgical site occurrences (SSOs) post cesarean delivery. SSOs include:

- Unanticipated local inflammatory response – measured by redness, tenderness, warmth, or induration on exam. This is a binary nominal categorical variable that will be measured as a repeated measure.

- Prolonged drainage – measured as drainage from surgical skin site  $\geq 3$  days from time of surgery. This is a binary nominal categorical variable that will be measured as a repeated measure.
- Fluid collection – measured as need for skin opening to drain fluid collected (seroma) underneath the skin wound. This is a binary nominal categorical variable that will be measured as a repeated measure.
- Dehiscence – measured as opening of skin wound  $\geq 2$ mm. This is a binary nominal categorical variable that will be measured as a repeated measure.
- Surgical site infection (SSI) - measured by redness, tenderness, warmth, or induration on exam with subject fever or purulent drainage. This is a binary nominal categorical variable that will be measured as a repeated measure.

The results of statistical procedure(s) will be presented as odds ratios with 95% confidence intervals, and number-needed-to-treat.

Missing data will be handled (e.g., type of imputation technique, if any, and provide justification), and approach to handling outliers, nonadherence and lost to follow-up by reporting this data as missing (and the reason why) and including all available data in the analysis.

---

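### Sections 4.1 and 6.3 contradict each other on whether patients' reports can establish the primary endpoint, and the chart route in 8.1/8.2 does not require the 9.4.2 criteria to be recorded

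*Protocol*

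**What the plan says.** **Who establishes an event.** Section 4.1 concedes that the dressings cannot be masked. Its protection against participant ascertainment bias is that SSO/SSI and the need for SII are "determined by skilled resident and attending physicians at each of the routine visits, not by patient report". Section 6.3 says: "Subjective outcomes (SSI/SSOs) are reported by patients or observed by study personnel, who cannot be blinded because they need to check the dressings". The same section also says that outcome assessors will be masked and that a blinded statistician will determine the primary outcome from the data.

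**How the findings reach the trial.** Section 8.1 makes the day 7–14 and day 42 ± 10 visits part of standard care, with the incision assessed by residents and attending physicians, and continues: "Charts will be reviewed to ascertain if SSO/SSIs were diagnosed or SII were necessary". For unscheduled visits, "information regarding the type of SSO or SII required will be obtained from review of the medical chart". Sections 8.1 and 8.2 both list, under data taken from existing records, "Incision assessment information from residents and attendings at follow-up visits".

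**What counts as an event.** Section 9.4.2 sets component rules:
- Dehiscence is "measured as opening of skin wound" of at least 2 mm.
- Prolonged drainage is drainage at 3 or more days from surgery.
- Local inflammatory response is any of redness, tenderness, warmth or induration.
- Fluid collection is the need to open the skin to drain it.
- SSI is one of those local signs together with fever or purulent drainage.

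Section 8.1 defines SSI differently, by a list of signs joined by and/or, with no minimum combination.

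**When forms are completed.** The schedule of activities (1.3) has incision assessments on post-operative day 1, at day 7–14 and at day 42. It marks CRF completion only at Visit 1 and Visit 4. Section 10.1.9.1 provides visit worksheets as source documents but does not say what they record.

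**The concern.** Caregivers and patients know the arm, so the validity of the SSO comparison depends on a fixed rule for who declares an event and on what evidence. Section 4.1 offers the exclusion of patient report as a safeguard, and 6.3 removes it. A woman's own account of redness or drainage is open to influence from knowing which dressing she wore, and the PICO group also has a compliance call on day 5 or 6 that the control group does not have.

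The second difficulty is the fit between definition and data. A routine note recording a small separation does not show whether the opening reached 2 mm. A note recording a wound infection does not show whether the 8.1 list or the 9.4.2 combination was met. If such notes are interpreted afterwards by people who know the allocation, the classification errors need not be equal in the two arms. SSI is directly affected, because 9.1 states a superiority hypothesis for it.

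**Working it through.** **1. Are the statements compatible?**
- 4.1 against 6.3: one excludes patient report and the other names it as a source. They are incompatible as written.
- 4.1 against 8.1: physicians diagnose at the visit, and chart review retrieves those diagnoses. These are compatible. The contradiction is therefore two-way, and it lies in one sentence of 6.3.

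**2. Does the collection route secure the 9.4.2 items?**
- Opening of at least 2 mm: nothing in 8.1 or 8.2 requires a measurement. This is the main gap.
- Individual local signs: not required item by item. Any one sign is enough for an SSO, so the gap matters when a note is non-specific.
- Drainage at 3 or more days: drainage seen at day 7–14 already passes. Only drainage that stopped before that visit needs a date.
- Fever: temperature is a listed vital sign (8.2), scheduled at Visits 2, 3 and 4 (1.3). Secured at those visits.
- Fluid collection: defined by a procedure, which a chart would ordinarily show.

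**3. Do the two SSI rules differ in effect?** Under 9.4.2, one local sign without fever or purulent drainage is a local inflammatory response. It is an SSO but not an SSI. Under 8.1 the same finding could be called an SSI. The mismatch therefore affects the SSI component more than the composite. The composite can differ for isolated fever, isolated odor, or fluctuance without skin opening.

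**4. The plan's own figure (9.2).** Inputs: 18% v 8%, alpha 0.05 (taken as two-sided), 80% power, 1:1 allocation. With mean risk 0.13:

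n = [1.96·√(2·0.13·0.87) + 0.8416·√(0.18·0.82 + 0.08·0.92)]² / 0.10² = [1.96·0.4756 + 0.8416·0.4703]² / 0.01 ≈ 176.4, so 177 per group.

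The plan states 180, and 180/0.90 = 200. Power at 180 is 80.8% by the normal approximation and 82.0% by exact enumeration of the chi-square test. The plan's figure reproduces.

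**5. Illustration of equal under-capture.** Multiply both risks by an assumed capture proportion s and keep 180 per arm:

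| s (assumed) | Standard | PICO | Exact power | Normal approximation |
|---|---|---|---|---|
| 1.0 | 18.0% | 8.0% | 82.0% | 80.8% |
| 0.9 | 16.2% | 7.2% | 77.0% | 75.9% |
| 0.8 | 14.4% | 6.4% | 71.2% | 70.2% |
| 0.7 | 12.6% | 5.6% | 64.7% | 63.7% |

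**6. Illustration of unequal capture.** Suppose there is no true effect (18% in both arms), with full capture on standard dressing and 80% on PICO (0.18 × 0.8 = 14.4%). The chance of a significant result favouring PICO is then about 15%, against a nominal 2.5% in that direction. At 90% capture on PICO (16.2%) it is about 6.6%.

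**The case against.** The case on the other side has real force, and several stronger readings fail against it.

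- *A reader might infer three competing sources.* The text does not support this. Chart review is how the clinicians' diagnoses are collected, and 8.1 says so within one paragraph.
- *A reader might infer that a vague note is scored as no event, so that events will certainly be missed.* No section says so. Section 9.4.2 has missing data reported as missing with the reason, and 10.1.8 sends gaps and anomalies back to the site. The supportable statement is that events can be missed.
- *A reader might take the remark in 8.2 about having no study-specific procedures to mean the items will not be recorded.* That sentence explains why no results are returned to patients and says nothing about recording.
- *The worksheets may already hold the items.* They may. Their content is unstated, and form detail often sits in the CRF or the manual of procedures. But nothing ties them to the 9.4.2 criteria, and the schedule marks no CRF at the post-operative day 1 or day 7–14 assessments.
- *The power losses rest on invented capture rates.* True. They also assume that the 18% planning rate reflects complete capture. If the studies behind it used routine ascertainment, some or all of the loss is already built in.

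Two points remain after these objections: the contradiction over patient report, and the missing requirement to record the criteria that define the endpoint. The statement in 6.3 that assessors are masked does not remove the concern about knowledge of the arm, because the same section says the personnel observing these outcomes cannot be blinded.

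**Conclusion.** The point holds in a limited form. Sections 4.1 and 6.3 contradict each other on whether a patient's report can establish a primary event. Sections 8.1 and 8.2 collect post-discharge findings from routine charts without requiring the 9.4.2 items, above all the opening in millimetres and the individual signs. Sections 8.1 and 9.4.2 define SSI by different rules. SSOs can therefore be missed or classified inconsistently by people who know the arm.

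The size of the effect is not known. The figures of 77%, 71% and 65% power, and the 15% false-positive chance under unequal capture, are illustrations that rest wholly on assumed capture rates. The sample size in 9.2 needs no correction on this account. The change should be made, but the defect does not by itself invalidate the design.

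**What to change.** 1. State one source in 4.1, 6.3 and 8.1: examination by the clinician already seeing the incision. Say that a patient's report alone is not an event, and remove patient report as a source from 6.3.
2. Reconcile the SSI definitions in 8.1 and 9.4.2 so that a single definition applies throughout.
3. Require the visit worksheet or CRF, in both arms, at every scheduled incision assessment and every unscheduled wound visit, and mark this in the schedule of activities. It should record the 9.4.2 items: opening in millimetres, drainage dates, each local sign yes or no, temperature, purulent drainage, and whether the skin was opened to drain fluid.
4. Derive the SSO and its components from that record by a written rule.

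If the existing worksheets already hold these items, step 3 reduces to saying so and correcting the schedule. The cost is otherwise one short form and about a minute per existing visit, with no added visits or assessors.

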## 8.2 SAFETY AND OTHER ASSESSMENTS

Sequence of events that will occur during screening process:

1. Review of scheduled cesarean delivery schedule for the day.
  - a. Screening procedures must be performed within 10 days of study enrollment.
2. Review of medical charts to assess for eligibility (see below).
3. Approach patient and explain trial and interventions.
4. No dietary or activity considerations are required for participation in the trial; however, patients will be counseled that the PICO dressing protocol requires the dressing to be in place for a minimum of 5 days.
5. Assessment of ability to comply with study intervention.
6. Obtain consent.
7. The patient will not be randomized until presentation to labor and delivery and randomization group will not be exposed to healthcare team until as close as possible to the end of the surgical procedure.

Information that will be obtained through review of existing data (i.e. patient's medical chart):

- Age
- BMI (kg/m^2)
- Medical comorbidities
- Pregnancy history (term, preterm, abortions, and living history)
- Mode of prior deliveries, if applicable
- Indication for cesarean delivery
- Incision assessment information from residents and attendings at follow-up visits

No study specific procedures will be performed and so no results will be provided to patients.

List and description of the following procedures/evaluations, as applicable:

- **Physical examination:** height and weight, fundal height, fetal heart rate measurement (initial study day prior to administration of intervention, and incision assessment).
- **Vital signs:** temperature, pulse, and blood pressure.
- **Assessment of adverse events.** Adverse events will be followed by attending physicians and research PI [name]. There are minimal expected adverse events that are not beyond the potential adverse events that could occur from the regular standard dressing (i.e. dressing tape site reaction or allergy to tape)

## 8.3 ADVERSE EVENTS AND SERIOUS ADVERSE EVENTS

### 8.3.1 DEFINITION OF ADVERSE EVENTS (AE)

Adverse event means any untoward medical occurrence associated with the use of an intervention in humans, whether or not considered intervention-related (21 CFR 312.32 (a)).

### 8.3.2 DEFINITION OF SERIOUS ADVERSE EVENTS (SAE)

An adverse event (AE) or suspected adverse reaction is considered "serious" if, in the view of either the investigator or sponsor, it results in any of the following outcomes: death, a life-threatening adverse event, inpatient hospitalization or prolongation of existing hospitalization, a persistent or significant incapacity or substantial disruption of the ability to conduct normal life functions, or a congenital anomaly/birth defect. Important medical events that may not result in death, be life-threatening, or require hospitalization may be considered serious when, based upon appropriate medical judgment, they may jeopardize the participant and may require medical or surgical intervention to prevent one of the outcomes listed in this definition. Examples of such medical events include allergic bronchospasm requiring intensive treatment in an emergency room or at home, blood dyscrasias or convulsions that do not result in inpatient hospitalization, or the development of drug dependency or drug abuse.

### 8.3.3 CLASSIFICATION OF AN ADVERSE EVENT

#### 8.3.3.1 SEVERITY OF EVENT

For adverse events (AEs) not included in the protocol defined grading system, the following guidelines will be used to describe severity:

- **Mild** – Events require minimal or no treatment and do not interfere with the participant's daily activities.
- **Moderate** – Events result in a low level of inconvenience or concern with the therapeutic measures. Moderate events may cause some interference with functioning.
- **Severe** – Events interrupt a participant's usual daily activity and may require systemic drug therapy or other treatment. Severe events are usually potentially life-threatening or incapacitating. Of note, the term "severe" does not necessarily equate to "serious".

